2.5.5.1 Mis-stratification

For randomization stratification that is done incorrectly due to transcription error or inconsistent site and central reviewer readings, primary analysis described in [Section 2.5.2](#) will be repeated using the final data entered in the clinical database, instead of the stratification factors in IVR system.

2.6 Analysis of secondary efficacy objective(s)

2.6.1 Secondary endpoints

The secondary efficacy variables are –

1. Change from baseline in individual cognitive domains (memory, executive function, and attention) as assessed by the individual components of the cognitive assessment battery at 3 years.
2. Change from baseline in the summary score of the instrumental activities of daily living (IADL) as assessed with Functional Activity Questionnaire (FAQ) at 3 years.

Composite scores for three main subdomains memory, attention and psychomotor function will also be generated by combining the standardized change from baseline scores for individual tests from the CCB using the following formulae:

- Composite score of memory tests = average of (Z_{CPAL} , Z_{ISLT} , $Z_{ISLT-DR}$)
- Composite score of executive function tests = average of (Z_{ONB} , Z_{GMLT})
- Composite score of attention tests = average of (Z_{DET} , Z_{IDT})

Each composite score will be the average of the non-missing individual test z-scores.

2.6.2 Statistical hypothesis, model, and method of analysis

For secondary efficacy variables composite z-scores by individual domain (memory, executive function and attention) and IADL, the changes from baseline to 3 years will be analyzed using the same repeated measures ANCOVA model as described in [Section 2.5.2](#) but with baseline GCCS replaced with respective secondary variable baselines. The adjusted mean changes at 3 years (Week 156) within each treatment, the difference in mean changes at 3 years (Week 156) between two treatments, its 95% confidence interval obtained from the above model will be presented. In addition, the treatment difference (LCZ696-valsartan) in mean changes from baseline to 3 years will also be expressed in terms of a standardized effect size (Cohen's d) with a 2-sided 95% confidence interval. The Cohen's d will be estimated as in a similar manner as planned for the primary endpoint analysis ([Section 2.5.2](#)). The analysis is based on likelihood method with an assumption of missing at random for missing data, and will be performed in the Safety set including 'on-treatment' data collected prior to the start of treatments for AD or cognitive impairment. On-treatment data are those collected while patients are on-study-

medication (regardless of treatment interruption) or within three months after final study drug intake date. This analysis will be performed in the SAF.

In addition, as supportive analysis, similar repeated measure ANCOVA model will also be performed for these secondary endpoints for all data in the FAS.

Summaries of absolute values and change from baseline by treatment group and visit will be presented. Figures will be produced to visually show the endpoint values (composite z scores by cognitive domain and IADL) by visit over the study period for each treatment group.

These analyses will be done in both SAF and FAS, for 'on-treatment' data and for all data, respectively.

2.6.3 Handling of missing values/censoring/discontinuations

As in the primary analysis, the analysis methods for secondary endpoints are consistent under the assumption of 'Missing at random'.

2.6.4 Sensitivity analysis for mis-stratification

For randomization stratification that is done incorrectly due to transcription error or inconsistent site and central reviewer readings, analysis described in [Section 2.6.2](#) will be repeated using the final data entered in the clinical database, instead of the stratification factors based on IVR system.

2.7 Safety analyses

Safety evaluations to be analyzed are listed as below:

- Change from baseline in a cortical composite SUV_r (standardized uptake value ratio) at 3 years

2.7.1 Change from baseline in SUV_r at 3 years

PET amyloid brain scans will be performed at randomization visit, at 18 months, and at end of study visit (scheduled at 3 years) for the patients participating the PET imaging sub-study and with non-missing baseline. In addition, for patients who have premature permanent discontinuation of study drug, it is planned to obtain an end-of-treatment PET scan if the next scheduled PET scan is < 6 months after treatment discontinuation. In order to make the most use of data collected from all available PET scan assessments, including the planned 'end-of-treatment' and 'end-of-study' assessments, the analysis of change from baseline (randomization) in a cortical composite SUV_r at 3 years (Week 156) will be based on a model-based multiple imputation approach under the MAR (missing at random) assumption. Further sensitivity analyses will be provided to assess the robustness of the MAR assumption on the missingness

mechanism. Following table provides an overview of missing data handling for cortical composite SUVr data with corresponding assumptions on missingness.

Table 2-4 Overview of missing data handling in analysis of change from baseline in SUVr at 3 years

Analysis	Analysis Set	Data excluded	Missingness assumption	Analysis method	Time points included	Imputed dataset required?
Estimand: The treatment effect had all patients stayed 'on-treatment' for the 3-year planned follow-up duration (Under 'as-treated' principle)						
Primary	SAF (restricted to PET imaging substudy)	Off-treatment (>6 months after last dose)	MAR	MI followed by ANCOVA	Baseline, Month 18, Year 3, and all other post-BL measurements <= 6 months after last dose	Yes
Sensitivity	SAF (restricted to PET imaging substudy)	Off-treatment (>6 months after last dose) Data outside 6-months window from scheduled visit	MAR	Repeated measure ANCOVA	Month 18, Year 3	No
Sensitivity	SAF (restricted to PET imaging substudy)	Off-treatment (>6 months after last dose)	MNAR for missing due to death, HF hospitalization and stroke - tipping point analysis	MI (tipping point analysis) followed by ANCOVA	Baseline, Month 18, Year 3, and all other post-BL measurements <= 6 months after last dose	Yes
Estimand: Measurement of treatment effect of interest MAR = Missing At Random; MNAR = Missing Not At Random; MI = Multiple Imputation						

The imputation model will include age stratification factor, MMSE stratification factor, region, baseline cerebrovascular disease burden, APOE4 status (carrier vs non-carrier), baseline amyloid status (positive/negative) and time (when the SUVr is assessed in days) as fixed effects with random intercept and slope (time) and a common unstructured covariance. This will be done separately within each treatment. Missing values will be imputed by the predicted values following from the fitted imputation model with random effects and random errors simulated from their respective distributions. SAS proc MCMC is used to impute missing values described above.

This imputation process will first create multiple imputations of missing SUVr at 3 years under a MAR assumption, resulting in multiple complete data sets after combining the imputed missing SUVr at 3 years values with the available SUVr at 3 years (so every patient with baseline SUVr in these multiple complete data sets will have an SUVr value at 3 years). An ANCOVA model using change from baseline to 3 years in SUVr as response variable, with treatment, age stratification factor, MMSE stratification factor, region, baseline cerebrovascular disease burden, APOE4 status, baseline amyloid status as factors and baseline SUVr value and treatment-by-baseline SUVr interaction as covariates will be run on each of these multiple completed data sets. Overall results and inference, including adjusted mean change at 3 years within each treatment, the difference in mean change at 3 years between two treatments, its 95%

confidence interval, are obtained by applying Rubin's rules on the estimates obtained from the imputed/completed data sets.

If convergence issue arises, the imputation model will be modified by replacing the common unstructured covariance with a common compound symmetry covariance between treatment groups. If convergence issue remains after implementing the compound symmetry covariance matrix, the model will be simplified by removing baseline cerebrovascular disease burden as explanatory factory from the model.

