### **Analysis on change from baseline in SUVR at 3 years**

In order to make the most use of data collected from all available PET scan assessments, including the planned ‘end-of-treatment’ and ‘end-of-study’ assessments, the analysis of change from baseline (randomization) in a cortical composite SUVR at 3 years (Week 156) will be based on a model-based multiple imputation approach under MAR (missing at random) assumption.

The imputation model will include age stratification factor, MMSE stratification factor, region, baseline cerebrovascular disease burden as measured by MRI, APOE4 status (carrier vs non-carrier), and time (when the SUVR is assessed in days) as fixed effects with random intercept and slope (time) and a common unstructured covariance. This will be done separately within each treatment by baseline amyloid status (positive/negative). This imputation process will first create multiple imputations of missing SUVR at 3 years under a MAR assumption, resulting in multiple complete data sets after combining the imputed missing SUVR at 3 years values with the available SUVR at 3 years (so every patient with baseline SUVR in these multiple complete data sets have an SUVR value at 3 years).

An ANCOVA model using change from baseline to 3 years in SUVR as response variable, with treatment, age stratification factor, MMSE stratification factor, region, baseline cerebrovascular disease burden as measured by MRI, APOE4 status, baseline amyloid status as factors and baseline SUVR value as covariate will be run on each of these multiple completed data sets. Overall results and inference, including adjusted mean change at 3 years within each treatment, the difference in mean change at 3 years between two treatments, its 95% confidence interval, are obtained by applying Rubin’s rules on the estimates obtained from the imputed/completed data sets.

[figure not shown]

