		5. Details are added in safety related sections after dry run review.		Section 2.7.1 : (1) There are very limited patients with positive baseline amyloid status, and imputation cannot be done for this stratum. Therefore, baseline amyloid status is included in the imputation model as factor instead. (2) SAS proc MCMC programing detail is provided. Section 2.7.2 : (1) specify analysis set for run-in epoch and double-blind randomized treatment epoch.
				 Section 2.7.3 : Remove “confirmed by adjudication committee” because death is not adjudicated.
		6. Visits numbers are updated in plasma Aβ1-40 to be consistent with		 Section 2.11 : Week 13, 52, 104 and Week 156 are the post-baseline scheduled visits for plasma Aβ1-40 assessments.

Date	Time point	Reason for update	Outcome for update	Section and title impacted (Current)
		protocol assessment schedule Table 6-1.		Analysis set for plasma Aβ1-40 is PET substudy set with non-missing baseline.
		7. Updates related to protocol deviations impacting analysis sets		
(1) Deviation ID OTH02 in Table 5-1: Site has been closed down for GCP reasons are not excluded from Safety set (SAF).
 
(2) Per clinical review: EXCL01, EXCL13, EXCL23, EXCL24, EXCL25, EXCL26, EXCL27, TRT07 are removed, and OTH21 is added in Table 5-1.
 
(3) Table 5-2 is updated to be aligned with Table 5-1.

		8. Additional statement for different endpoints PET substudy set		
Section 2.2: Separate flag will be create for different endpoint due to non-missing baseline condition for PET substudy set

		9. Remove subgroup analysis for disposition related summary, add 3 subgroups for CogState GCCS, minor update to NYHA category, and remove Central America from Latin America definition		
Table 2-1: (1) CTT reviewed and decided to remove the subgroup analyses of disposition from CSR; (2) Randomization baseline SBP ≤140 and >140 mmHg subgroup, Age < 65 and ≥ 65 subgroup, and diabetes mellitus status at screening (Yes, No) subgroup are added for CogState GCCS endpoint; (3) subgroup categories of NYHA class at randomization are: I/II versus III/IV; (4) update Latin America to remove “including Central America” because no Central America countries participated in the study.

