3.2 Sample size calculation for the PET imaging substudy

Approximately 300 complete patients (in 1:1 allocation ratio to LCZ696 and valsartan) will provide at least 80% probability that the 2-sided 95% CI excludes a between-treatment absolute difference of 0.01 (corresponding to an incremental 33% increase in LCZ696 vs. valsartan) in change from baseline in SUVr over 3 years if there is no expected difference between two treatments. This calculation is based on the assumptions that the mean change over 3 years from baseline in SUVr is 0.03 in the control group, the common standard deviation is 0.03 (estimated from ADNI data, [Chen et al 2015](#)). It is noted that the ADNI data presented in Chen's paper are by patients' cognitive status (normal, MCI, dementia) and for changes over two years. The assumptions used here are guestimates from the 2 year data in normal cognitive and MCI subjects.

An absolute difference in SUV ratio of 0.01 was considered small as it represents a value that is lower than the rate of SUVr change that distinguishes between amyloid positive and negative patients (0.026 vs. 0.011).

Sample size calculation was performed using N-Query 7.0.

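### The SUVr imputation model gives amyloid-positive and amyloid-negative patients the same average slope; an amyloid-by-time term is a cheap improvement

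*SAP*

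**What the plan says.** SAP 2.7.1 imputes missing 3-year SUVr from a mixed model whose fixed effects include "baseline amyloid status (positive/negative) and time (when the SUVr is assessed in days) as fixed effects with random intercept and slope". Table 2-4 counts baseline among the time points, so the modelled response is the SUVr value over time, not the change. On the level of fitting, the SAP says: "This will be done separately within each treatment". Missing values are "predicted values following from the fitted imputation model with random effects and random errors simulated from their respective distributions". No amyloid-by-time term is listed.

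Protocol 9.5.2 lists nearly the same terms, but fits them by stratum: "This will be done separately within each treatment by baseline amyloid status (positive/negative").

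The SAP document history explains the move: "There are very limited patients with positive baseline amyloid status, and imputation cannot be done for this stratum". Status was made a factor in the model instead.

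SAP 3.2 justifies the 0.01 margin as smaller than "the rate of SUVr change that distinguishes between amyloid positive and negative patients", and gives 0.026 and 0.011 without a time unit.

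After imputation, the 2.7.1 ANCOVA has change from baseline as its response and amyloid status as a factor.

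**The concern.** In a model for SUVr level with a random intercept, a main effect of amyloid status describes where positives start, not how fast they move. The protocol's stratum-specific fit gave each stratum its own slope. Pooling the strata with status as a main effect forces one mean slope per arm, although the plan itself quotes different rates. The imputation model is then more restrictive than the ANCOVA it feeds, which does let change differ by status.

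At stake is the imputed change in positives. If positives go missing more often in one arm, that arm's mean change is understated. If that arm were LCZ696, the amyloid comparison, which is a safety endpoint, would move toward no difference.

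**Working it through.** **The plan's own figure.** SAP 3.2 uses a margin of 0.01, SD 0.03 and a two-sided 95% CI. Per arm, n = 2 x (1.960 + 0.842)^2 x 0.03^2 / 0.01^2 = 141.3, so 142, or 284 in total. With 150 per arm the SE is 0.03 x sqrt(2/150) = 0.0035 and the probability is 82.3%. Then 300 / 0.70 = 429. The stated figures of about 300 completers, at least 80% and about 430 randomized reproduce.

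**Rates.** 0.026 / 0.011 = 2.36.

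**Pooled slope.** With positive share p, pooled = p x 0.026 + (1 - p) x 0.011. At p = 10% this is 0.0026 + 0.0099 = 0.0125, and 0.0125 / 0.026 = 48%. The percentage does not depend on the time unit.

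**What positives are given.** I took the large-sample likelihood fit of the SAP model with scans at 0, 1.5 and 3 years. These inputs are assumptions, not in the documents:
- 15% of patients with a baseline scan only and 15% with baseline plus 18 months;
- baseline SD 0.05 and level gap between strata 0.20;
- error SD 0.010-0.015, with slope variance set so that 3-year change has SD 0.03;
- no correlation between intercept and slope within a stratum;
- random effects predicted from each patient's own scans.

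Results at 10% positive and error SD 0.010:

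| Rates read per | True 3-year change, positives | Pooled | Imputed, baseline scan only | Imputed, baseline + 18 months |
|---|---|---|---|---|
| 3 years | 0.026 | 0.0125 | 0.0126 | 0.0207 |
| 2 years | 0.039 | 0.0187 | 0.0188 | 0.0311 |
| 1 year | 0.078 | 0.0375 | 0.0377 | 0.0636 |

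An 18-month scan brings positives to about 80-82% of their true change, or 69-71% at error SD 0.015. With an amyloid-by-time term the imputed means equal the assumed truth.

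**Arm mean when missingness ignores status.** On the 3-year reading at 10%, positives fall short by 0.0135 and negatives are over by 0.0015. Then 0.10 x 0.0135 = 0.90 x 0.0015 = 0.00135, so the errors cancel. The fitted model also gives zero bias with 40% missing in one arm and 20% in the other.

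**Arm mean when it does not.** Half the positives are missing in one arm and 30% of all other patients are missing (error SD 0.010). Size of the shift in the treatment difference, for rates read per 3 / 2 / 1 years:

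| Positive share | Missing positives split evenly between the two scan patterns | All with baseline scan only |
|---|---|---|
| 5% | 0.0001 / 0.0002 / 0.0004 | 0.0003 / 0.0004 / 0.0008 |
| 10% | 0.0002 / 0.0004 / 0.0007 | 0.0005 / 0.0008 / 0.0016 |

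The range 0.0001-0.0016 is 1-16% of the 0.01 margin, and at most 0.0016 / 0.0035 = 0.46 of the planned SE.

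**The case against.** The strongest reply is that the treatment comparison is well protected, and most of it stands. Randomization is stratified on amyloid status, positives are few, and both arms use the same model. Nothing in the documents suggests that missingness differs by status and arm.

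SAP 2.7.1.1 also plans two relevant analyses. One repeats 2.7.1 without patients who have no post-baseline scan, which removes the worst-affected group; positives with an 18-month scan are still partly shrunk. The other is a repeated-measures model for change with amyloid status as a factor. It allows a different change by status, but as one offset common to both visits, and Table 2-4 drops scans outside the 6-month window. Both are partial checks.

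The reply on feasibility also has force: the model was changed because the positive stratum could not be imputed and convergence failed. That justifies pooling the other terms. It does not show that one interaction term with a prior is infeasible.

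A reader might go further in four ways that the documents do not support:
- **Every imputed positive gets the pooled rate.** The model has a random slope, so this is true only without a post-baseline scan, or if random effects were drawn ignoring the patient's own scans. The SAP text does not settle the latter.
- **The bias could be a large part of the margin.** At 30% positive the same scenarios reach 0.0040. That share conflicts with the document history's account of how few positives there are. With annual rates it also implies a pooled change of 3 x 0.0155 = 0.0465, against the assumed control mean of 0.03.
- **An amyloid-status subgroup result for SUVr is flattened.** Table 2-1 lists the subgroup in general terms, but SAP 2.2.1 leaves the choice of parameters to their own sections, and the visible text of 2.7.1 and 2.7.1.1 describes no such analysis.
- **APOE4 needs a time term too.** The protocol model had none either, and no APOE4-specific rate is quoted.

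**Conclusion.** A cheap improvement, not a threat to the main SUVr conclusion. The imputation model omits a slope difference that the protocol's fit allowed, that the plan's own rates imply, and that the ANCOVA assumes possible. Positives without a post-baseline scan receive about 48% of their expected change at 10% positive; those with an 18-month scan receive about 69-82%. The treatment difference is unaffected if missingness is unrelated to status, and shifts by about 0.0001-0.0016 in the unfavourable scenarios at 5-10% positive.

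The sizes rest on the assumed positive share, missingness patterns and error SD, and on the time unit. A 3-year reading cannot give the assumed control mean of 0.03, since even positives reach only 0.026. A 2-year reading needs (0.03 - 0.0165) / 0.0225 = 60% positive. An annual reading, at 0.033 or more, is nearest with few positives, so the upper part of each range is the more relevant.

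**What to change.** Add an amyloid status-by-time fixed effect to each arm's PROC MCMC imputation model, with a weakly informative prior stated in the SAP because positives are few. State that random effects are drawn conditional on each patient's observed scans. SAP Section 4 reports no change to protocol-specified analyses, so note there that the stratum-specific fit was replaced.

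The cost is one parameter per arm. The interaction will be imprecise and influenced by its prior, and there is some convergence risk; add this term to the existing fallback sequence. Sharing one interaction across arms would be more stable, but it needs a joint two-arm model and would pull any drug effect specific to positives toward zero in the imputed values, so arm-specific terms are preferable.

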2.7.1.1 Supportive analysis

Both the actual SUVr values and change from baseline values will be descriptively summarized for each treatment group by each assessment visit over study period by providing summary statistics (n, mean, SD, median, Q1, Q3, min, max). Additionally, number and percentage of patients with positive PET scan will be reported for each treatment group by each assessment visit. Available SUVr data at 'end of treatment' and 'end of study' will be summarized separately as above.

To assess the sensitivity of the primary analysis method results to the imputation model, a sensitivity analysis will be performed on the change in a cortical composite SUVr from baseline to 3 years by incorporating information from other assessments still under the assumption of MAR. The change from baseline in SUVr will be analyzed based on a repeated measures ANCOVA model in which treatment, age stratification factor, MMSE stratification factor, region, baseline cerebrovascular disease burden, APOE4 status (carrier vs. non-carrier), baseline amyloid status (positive/negative), visit (18 months, 3 years), and treatment-by-visit interaction will be included as fixed-effect factors and baseline value and baseline-by-treatment as covariates, with a common unstructured covariance matrix among visits between treatment groups. The adjusted mean changes at 3 years (Week 156) within each treatment, the difference in mean changes at 3 years (Week 156) between two treatments, its 95% confidence interval obtained from the above model will be presented. The analysis is based on likelihood method with an assumption of missing at random for missing data.

To assess the sensitivity of the primary analysis methods results to the baseline amyloid status (positive/negative) based on quantitative (numerical) cutoff instead of qualitative (visual) assessment, a sensitivity analysis will be performed using the same ANCOVA model specified in [Section 2.7.1](#) but with the quantitative positive/negative assessment of the baseline brain amyloid status. A shift table to summarize the proportion of patients' amyloid status change over time from baseline i.e. patients transitioning from negative to positive based on quantitative assessment will also be provided by treatment group.

In addition, to assess the sensitivity of the analysis results to the MAR assumption used in the multiple imputation for primary analysis method, a tipping point analysis will be performed on the change from baseline in SUVr which assumes that missing values after death, HF hospitalization and stroke are missing not at random (MNAR). This analysis will follow the same procedure as described in [section 2.5.5](#) for the primary endpoint, with the exception that the imputations under MAR are obtained from a regression based imputation as described in the primary analysis method of this endpoint ([Section 2.7.1](#)). The analysis will be repeated for varying penalty factors in a range between 1 and 1.6.

[figure not shown]
If convergence issue arises in any of above described supportive analyses, the handling approach described in [Section 2.7.1](#) will be used to address the convergence issue.

[figure not shown]
Furthermore, to assess the sensitivity of the analysis results to the randomization stratification that is done incorrectly due to transcription error or inconsistent site and central reviewer readings, analysis described in [Section 2.7.1](#) will be repeated using the final data entered in the clinical database, instead of the stratification factors based on IVR system.

[figure not shown]
To address missing assessments due to COVID-19 pandemic, the analysis mentioned in [Section 2.7.1](#) will be repeated using PET substudy set with a wider assessment window extending from 6 months to 9 months for assessments that are scheduled to take place starting Mar 1, 2020 and onwards. This also applies to the data excluded from analysis if assessment is done more than 9 months after last study drug intake instead of 6 months.

[figure not shown]
All analyses will be performed in patients in the Safety set who participate in the PET image substudy and with non-missing baseline, including ‘on-treatment’ data only. On-treatment data refer to the SUVr values obtained while patients are on-study-medication (regardless of treatment interruption), or within defined window in each supportive analysis (six months or nine months) after the final study drug intake date.

In addition, for patients who do not have any post-baseline SUVr assessments and part of the reason is due to concerns over exposure to COVID-19 by visiting the site, the analysis mentioned in [Section 2.7.1](#) will be repeated using PET substudy set excluding patients without any post-baseline assessments, including ‘on-treatment’ data only (within six months after the final study drug intake date).

[figure not shown]

[figure not shown]
[figure not shown]

